## **Study Protocol**

The purpose of the proposed study is to conduct a study on individuals with lower limb amputation evaluating if residual limb fluid volume data collected using a novel non-invasive device is beneficial towards prosthetic prescription, fit, and comfort as determined by amputee test subjects and practitioners (prosthetists). Residual limb volume/mass changes typically affect prosthetic limb fit of people with limb amputation, and changes in limb volume/mass can put the limb at risk of injury and preclude use of the prosthesis.

Participants' residual limb fluid volume will be monitored through segmental bioimpedance analysis both before and after a practitioner-issued modification to the prosthesis as an observational cohort study and a blinded randomized clinical trial in which the data may or may not be shared with the practitioner before the modification is made to the prosthesis.

The Specific Aims are to:

[figure not shown]
Aim 1. Characterize residual limb volume accommodation strategies and associated clinical outcomes experienced by prosthetic users with different activity/volume profiles. Changes in users' limb volume, prosthetic fit, performance, and satisfaction will be used to determine which strategies are most predictive of positive clinical outcomes. This aim will be accomplished using an Observational Cohort Study.

Aim 2. Compare the effectiveness of bioimpedance-enhanced and traditional prosthetic evaluation, design, and fitting practices for lower limb participants who require adjustment or replacement of their volume management system. Differences in participants' limb volume, prosthetic fit, performance, and satisfaction will be used to assess if bioimpedance-enhanced fitting produces superior outcomes compared to traditional, experience-based fitting methods. This aim will be accomplished by using a Randomized Controlled Trial (RCT).

[figure not shown]
Primary quantitative data will be collected via custom study instruments, such as a bioimpedance measurement system to assess limb volume changes. Qualitative data will be collected from participants directly through self-report of their health history, during study procedures. All data for this research will be collected prospectively.

A more detailed timeline of the study procedures is given on the following pages.

# Aim 1

## Aim 2

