## **Statistical Analysis Plan**

### **Aim 1**

Aim 1 is an exploratory study with the objective of generating potential volume management strategies based on the measurement of limb fluid volume fluctuations via bioimpedance. As such, it does not involve statistical hypothesis testing per se, and therefore, no power analysis is involved. The primary outcome measure of socket comfort score (SCS), pre and post socket modification will be analyzed. A Shapiro-Wilk test will be used to determine normalcy. Normally distributed data will be compared using paired t-tests. If data is not normally distributed, a Wilcoxon Signed Rank Test will be used to make comparisons. A significance level of 0.05 will be used to determine whether measured differences in limb volume were statistically significant between interventions.

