### **Aim 2**

Data collected at each assessment (i.e., pre-implementation, 1-month follow-up, and 6-month follow-up) in Aim 2 will be visually analyzed using histograms and boxplots. Next, we will test data for normality using a Shapiro-Wilk test. If the data is found to be normally distributed, our hypothesis will be evaluated using clinical outcome measure scores (e.g., SCS) in a repeated-measures analysis of variance (rmANOVA) to assess differences in outcomes achieved by participants assigned to the treatment (i.e., bioimpedance-enhanced fitting) group vs. control (i.e., traditional fitting) group over time. In the event that data are not normally distributed, we will use a nonparametric Friedman test to assess differences in outcomes between bioimpedance-enhance and traditional fitting. Significance for statistical tests will be set at  $\alpha < 0.05$ . Our hypothesis will be evaluated using outcome variables of number of visits and total visit time. We will compare the total number of visits and total time over the 6-month period between the treatment and control groups using a t-test for independent samples.

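### Aim 2 pools adjustment and replacement cases but compares visits and visit time unadjusted; if type of need predicts these outcomes, precision is lost that one pre-allocation covariate could recover

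*Combined protocol and SAP*

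**What the plan says.** The Specific Aims in the Study Protocol define the Aim 2 population as "lower limb participants who require adjustment or replacement of their volume management system". Both kinds of need therefore enter a single randomised comparison of bioimpedance-enhanced and traditional fitting.

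The Aim 2 section of the Statistical Analysis Plan states: "Our hypothesis will be evaluated using outcome variables of number of visits and total visit time". It continues: "We will compare the total number of visits and total time over the 6-month period". The method named for this is a contrast "between the treatment and control groups using a t-test for independent samples". No covariate, stratum term or subgroup by type of need is named.

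The text does not describe the randomisation method, and the timeline figures are not shown. No sample size, power, effect size or SD is given for Aim 2. The remark that "it does not involve statistical hypothesis testing per se, and therefore, no power analysis is involved" belongs to Aim 1 only.

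**The concern.** A participant who needs a replacement may well need more visits and more time than one who needs an adjustment, whichever arm they are in. If so, two things follow.

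- **Precision.** The difference between the two kinds of need sits in the residual variance of the t-test. It widens the interval for the arm difference and lowers power.
- **Realised estimate.** If one arm happens to receive more replacements, the observed difference in visits moves by the imbalance multiplied by the gap between the types.

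Visits and visit time are more exposed than socket comfort score (SCS). SCS has a pre-implementation measurement. The documents describe no baseline counterpart for visits or time over 6 months.

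**Working it through.** The plan gives no Aim 2 figure to reproduce. Everything below is a sensitivity calculation on assumed inputs.

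**1. Variance explained, in visits**

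Assumed: adjustment mean 2 visits, SD 1; replacement mean 3 to 5, SD 1.5 to 2; share of replacements p from 0.3 to 0.5. With gap d between the means:

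R² = p(1−p)d² / [p(1−p)d² + p·SDr² + (1−p)·SDa²]

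Crossing all the assumed ranges gives these extremes:

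- Lowest: p = 0.5, d = 1, SDr = 2. The between-type part is 0.25 and the within-type part is 0.5×4 + 0.5×1 = 2.5. R² = 0.25/2.75 = 0.09.
- Highest: p = 0.4, d = 3, SDr = 1.5. The between-type part is 0.24×9 = 2.16 and the within-type part is 0.4×2.25 + 0.6×1 = 1.5. R² = 2.16/3.66 = 0.59.

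The standard error after adjustment is about √(1−R²) of the unadjusted one: √0.91 = 0.95 and √0.41 = 0.64. The cut is therefore about 5 to 36%. The equivalent gain in sample size, 1/(1−R²) − 1, is 2.75/2.5 − 1 = 10% to 3.66/1.5 − 1 = 144%.

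These figures assume a label that identifies the need perfectly. With an imperfect label, R² shrinks by the squared correlation between label and true need.

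**2. What this does to power**

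Let g be the gap in within-type SDs. The unadjusted SD is inflated by √(1 + p(1−p)g²). Assumed: two-sided alpha 0.05 (the SAP does not state sidedness), 80% power, 1:1 allocation and an effect of 0.8 within-type SD. With the type term, n per arm = 2(1.96 + 0.84)²/0.8² = 24.5, so 25. At p = 0.5:

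| g | R² | n per arm, unadjusted | unadjusted power at 25 per arm |
|---|---|---|---|
| 0.5 | 6% | 27 | 0.78 |
| 1.0 | 20% | 31 | 0.72 |
| 1.5 | 36% | 39 | 0.62 |
| 2.0 | 50% | 50 | 0.52 |

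Adjusted power at 25 per arm is about 0.81 (0.8×√12.5 − 1.96 = 0.87 on the normal scale). At p = 0.3 the unadjusted n per arm is 26, 30, 37 and 46.

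**3. Chance imbalance**

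Under unstratified 1:1 allocation with p = 0.5, the hypergeometric probability that the arms differ by 20 points or more in the share of replacements is:

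| Per arm | Probability |
|---|---|
| 10 | 66% |
| 20 | 34% |
| 30 | 20% |
| 50 | 7% |
| 100 | 0.7% |

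At the assumed gap of 1 to 3 visits, a 20-point imbalance moves the observed difference by 0.2×1 to 0.2×3, that is 0.2 to 0.6 visits.

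**4. Validity, and cost if need type is irrelevant**

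Simulation used normal outcomes with equal SDs, p = 0.5, 10 to 30 per arm and 6000 runs per setting. Type I error of the unadjusted t-test was 0.046 to 0.056, consistent with 0.05. With g = 0, power at 20 per arm was 0.70 unadjusted and 0.68 adjusted. With g = 1 it was 0.60 and 0.69.

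**The case against.** The strongest reply is that no error has been shown: an unadjusted t-test in a randomised trial is valid, and adjustment is an efficiency option. That stands. A reader might infer that the pooled comparison is biased or has an inflated false-positive rate, but the simulated type I error does not support this. Chance imbalance adds noise that can mislead in one realised trial; it does not bias the procedure.

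Four further points have force.

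- **Trial size.** A reader might assume that Aim 2 is small. The documents give no size, and the imbalance argument nearly vanishes at 100 per arm.
- **Size of the gap.** Nothing in the documents says that visits or time differ by type of need. At a gap of 0.5 SD, only 5 to 6% of the variance is at issue.
- **Timing.** A reader might infer that need type must be known at entry because it defines the population. The criterion can be met without deciding which need applies, and the final choice may be part of the fitting process being compared. A provisional label can still be recorded before allocation. It may be noisy, so the gain would be smaller, but little is lost by including it.
- **Allocation.** Stratification by need cannot be excluded, because the method is not described and figures are missing. Even then, the stratification factor belongs in the analysis, and the SAP names none.

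It is also tempting to extend the adjustment to SCS. The material does not support that: no benefit has been shown there, the repeated-measures analysis already uses the pre-implementation score, and the Friedman fallback takes no covariate.

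**Conclusion.** The concern holds in a conditional form, limited to visits and visit time. The mixed population and the unadjusted t-test are both in the text. The loss is one of precision, and it arises only if need type predicts these outcomes. Across the assumed visit inputs the recoverable part of the standard error is about 5 to 36%, and less with an imperfect label. No figure can be given for visit time, because the documents supply nothing to base one on. The imbalance risk matters at roughly 10 to 30 per arm without stratification, and is minor by 100. This is an inexpensive improvement to a valid analysis, of low severity; it does not call the planned comparison into question.

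**What to change.** Add one enrolment field, completed before allocation, for the provisional need (adjustment or replacement). In the SAP, replace the t-test for total visits and total visit time with a prespecified linear model with terms for arm and provisional need. State that the modification finally made must not be used as the covariate, because it follows allocation and may be influenced by the shared bioimpedance data. If allocation has not begun, also stratify by the provisional need. Leave the SCS analysis as it is on this point.

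The cost is the field, a few lines of SAP text and one degree of freedom per model (at 20 per arm, 38 becomes 37). If need type turns out to predict nothing, the power loss is very small.

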## **Statistical Analysis Plan**

### **Aim 1**

Aim 1 is an exploratory study with the objective of generating potential volume management strategies based on the measurement of limb fluid volume fluctuations via bioimpedance. As such, it does not involve statistical hypothesis testing per se, and therefore, no power analysis is involved. The primary outcome measure of socket comfort score (SCS), pre and post socket modification will be analyzed. A Shapiro-Wilk test will be used to determine normalcy. Normally distributed data will be compared using paired t-tests. If data is not normally distributed, a Wilcoxon Signed Rank Test will be used to make comparisons. A significance level of 0.05 will be used to determine whether measured differences in limb volume were statistically significant between interventions.

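### Aim 1 promises to find which accommodation strategies best predict good outcomes, but the paired pre/post SCS tests it names cannot link strategy or profile to outcome

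*Combined protocol and SAP*

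**What the plan says.** In the Study Protocol, Aim 1 covers accommodation strategies and the "clinical outcomes experienced by prosthetic users with different activity/volume profiles". Changes in limb volume, fit, performance and satisfaction "will be used to determine which strategies are most predictive of positive clinical outcomes". The design is stated plainly: "This aim will be accomplished using an Observational Cohort Study". Limb fluid volume is monitored "both before and after a practitioner-issued modification to the prosthesis".

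The Statistical Analysis Plan, Aim 1, describes the aim more modestly, as an "exploratory study with the objective of generating potential volume management strategies". It adds that "it does not involve statistical hypothesis testing per se, and therefore, no power analysis is involved". On the analysis it says: "The primary outcome measure of socket comfort score (SCS), pre and post socket modification will be analyzed". After a Shapiro-Wilk check, "Normally distributed data will be compared using paired t-tests"; otherwise a Wilcoxon signed-rank test is used. A last sentence sets a 0.05 significance level for limb-volume differences between interventions. It does not say what the interventions are and names no further test.

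**The concern.** Saying that some strategies predict good outcomes better than others is a statement about differences between strategies. A pre/post comparison of SCS answers another question: did comfort change, on average, after the socket was modified? The SAP text for Aim 1 shows no strategy factor, no profile term and no model relating either to a clinical outcome.

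If the plan is followed as written, the SCS analysis can support a statement that comfort improved after modification. It cannot support a statement that one strategy went with more improvement than another, or that this depended on the user's profile. Any such conclusion would rest on an estimate chosen after the data were seen. The tempting substitute is to run the paired test within each strategy and compare p-values. That does not estimate a difference between strategies, and it favours whichever strategy has the most participants.

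**Working it through.** The plan gives no figure to reproduce for Aim 1: no sample size, SD, effect size or number of strategies. The main check is therefore logical; the arithmetic after it is illustrative.

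**1. Aim against analysis.**

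| Needed for the protocol's Aim 1 | Visible in the SAP, Aim 1 |
|---|---|
| Outcome compared across strategies | SCS compared before and after modification, within person |
| Activity/volume profile | Not mentioned |
| Limb volume as one of the changes used | Limb-volume differences between interventions at the 0.05 level; interventions not defined |
| Estimate linking strategy to clinical outcome | None visible |

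The other methods in the SAP (repeated-measures ANOVA, Friedman test, independent-samples t-test) are assigned to Aim 2.

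**2. What a paired pre/post test uses.** Its only input is the set of within-person differences. If strategy or profile labels are reassigned among participants, those differences stay the same and so does the result. The test therefore cannot tell strategies apart.

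**3. Example (hypothetical effects, one strategy per person, equal groups).** True mean SCS changes of +2, +1 and 0 give a pooled change of (2 + 1 + 0)/3 = +1.0. Changes of +1, +1 and +1 give (1 + 1 + 1)/3 = +1.0. The best-minus-worst difference is 2 points in the first case and 0 in the second, yet the pooled mean is the same.

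**4. Precision of a model that does include strategy (all inputs assumed).** Let d be the SD of change, r the pre/post correlation, k the number of strategies and N the number of participants, with one modification each, equal pre and post SDs, and similar baseline SCS across strategies.

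- Residual SD after baseline adjustment = d × √((1 + r)/2). With d = 2 and r = 0.5: 2 × √0.75 = 1.732.
- 95% half-width for two strategies = t(0.975, N − k − 1) × residual SD × √(1/n₁ + 1/n₂). With N = 30 and k = 3 there are 26 degrees of freedom and t = 2.056.
- Groups of 10/10/10: 2.056 × 1.732 × √(1/10 + 1/10) = 2.056 × 1.732 × 0.447 = **1.59**.
- Groups of 20/5/5, the two small groups: 2.056 × 1.732 × √(1/5 + 1/5) = 2.056 × 1.732 × 0.632 = **2.25**.

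Range over other assumptions, equal groups:

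| Change made | Half-width |
|---|---|
| k = 3, 10 each, d = 2, r = 0.3 or 0.7 | 1.48 or 1.70 |
| k = 3, 20 each, d = 1.5, r = 0.5 | 0.82 |
| k = 3, 5 each, d = 3, r = 0.5 | 3.62 |
| N = 30, d = 2, r = 0.5, k = 2 or 5 | 1.30 or 2.06 |

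If baseline SCS differs between strategies the interval widens. In simulation of the 10/10/10 case with steps of 0.5 SD between adjacent strategies, the outer pair had a mean half-width of 1.76.

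**The case against.** The strongest reply is that the paired tests may themselves be the strategy contrast. The SAP's last sentence for Aim 1 refers to interventions in the plural, and the protocol's detailed Aim 1 timeline is not visible in the text available. If each participant experienced more than one intervention, a paired test could properly compare limb volume between them. Limb volume is also one of the changes that the protocol says will be used to judge strategies. This stands. A reader might infer that Aim 1 plans no comparison between strategies at all, or that strategies and profiles are nowhere defined. The documents do not support either inference. But even on the generous reading, that sentence does not connect strategy to SCS, which the SAP calls the primary outcome, and does not bring in profile.

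A second reply is that Aim 1 is exploratory and meant to generate strategies, while Aim 2 carries the comparative hypothesis. That lowers the severity. In the SAP, the exploratory label explains why there is no power analysis; it does not supply an estimate for the protocol's stronger wording, and the two statements of the objective are not reconciled.

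A third reply is that a model may deliver little. Groups formed by practitioners' choices are unlikely to be equal. In the 20/5/5 case the half-width of 2.25 exceeds the illustrative 2-point difference between best and worst strategy. Confounding by indication also remains. This stands too, and it is why a descriptive alternative belongs in the fix.

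**Conclusion.** The concern holds in a limited form. As introduced for SCS, the paired tests estimate average change and cannot show which strategy or profile goes with a better outcome. A limb-volume contrast between strategies may be intended, but nothing visible in the SAP links strategy to SCS or uses profile at all. This conclusion rests on the text alone and needs no assumed figure.

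Severity is minor to moderate: the aim is exploratory, and the mismatch affects what may be concluded from Aim 1, not the validity of the pre/post comparison itself. The precision figures (about ±1.6 SCS points with equal groups, about ±2.25 between the two small groups at 20/5/5) depend on assumed numbers and on one strategy per person. They show what an added analysis might offer and say nothing about the trial's actual precision.

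**What to change.** Keep the paired tests as descriptive and add one exploratory model to the SAP for Aim 1:

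- Regress post-modification SCS on accommodation strategy and pre-modification SCS. Add activity/volume profile where numbers allow, and a participant random effect if anyone contributes more than one modification.
- Fit the same model for change in limb volume.
- Report between-strategy differences with 95% confidence intervals, and do not rank strategies by p-value.
- Label the results hypothesis-generating, because modifications are practitioner-issued and not randomised in this cohort.
- State how residuals will be checked, since the signed-rank fallback has no counterpart in this model.

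If strategies are too many or too sparse to model, summarise outcomes by strategy and profile with confidence intervals, and revise the protocol's claim about prediction to match the SAP's objective of generating potential strategies. The SAP should also say what the interventions in its limb-volume sentence are and whether each participant receives more than one.

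The cost is SAP wording and a model fitted to data that the aim already needs. The drawbacks are wide intervals, further degrees of freedom spent on profile terms, and confounding by indication that baseline adjustment does not remove.

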### **Aim 2**

Data collected at each assessment (i.e., pre-implementation, 1-month follow-up, and 6-month follow-up) in Aim 2 will be visually analyzed using histograms and boxplots. Next, we will test data for normality using a Shapiro-Wilk test. If the data is found to be normally distributed, our hypothesis will be evaluated using clinical outcome measure scores (e.g., SCS) in a repeated-measures analysis of variance (rmANOVA) to assess differences in outcomes achieved by participants assigned to the treatment (i.e., bioimpedance-enhanced fitting) group vs. control (i.e., traditional fitting) group over time. In the event that data are not normally distributed, we will use a nonparametric Friedman test to assess differences in outcomes between bioimpedance-enhance and traditional fitting. Significance for statistical tests will be set at  $\alpha < 0.05$ . Our hypothesis will be evaluated using outcome variables of number of visits and total visit time. We will compare the total number of visits and total time over the 6-month period between the treatment and control groups using a t-test for independent samples.

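### In Aim 2 a Shapiro-Wilk result can decide whether clinical scores are compared between arms, because the non-normal branch is a Friedman test with no arm term

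*Combined protocol and SAP*

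**What the plan says.** The SAP section on Aim 2 begins with description: "Data collected at each assessment (i.e., pre-implementation, 1-month follow-up, and 6-month follow-up) in Aim 2 will be visually analyzed using histograms and boxplots". It continues: "Next, we will test data for normality using a Shapiro-Wilk test". Two branches follow.

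- **Normal:** "If the data is found to be normally distributed, our hypothesis will be evaluated using clinical outcome measure scores", with SCS as the example, in a repeated-measures ANOVA (rmANOVA) of "participants assigned to the treatment (i.e., bioimpedance-enhanced fitting) group vs. control (i.e., traditional fitting) group over time".
- **Not normal:** "In the event that data are not normally distributed, we will use a nonparametric Friedman test", which the SAP describes as assessing the difference between the two fitting methods.

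A separate sentence adds two further outcomes: "Our hypothesis will be evaluated using outcome variables of number of visits and total visit time". These are compared between arms by an independent-samples t-test, with no normality condition attached.

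The section does not say whether the Shapiro-Wilk test is run on pooled data, within arm or on residuals. It gives no rule for assessments or outcomes that disagree, and it does not mention sphericity.

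**The concern.** The two branches do not answer the same question. The rmANOVA has an arm factor and an arm-by-time term. The Friedman test asks only whether scores differ between visits within participants. A preliminary test on the outcome data can therefore decide whether the scores are compared between randomised arms.

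Three features of the gate add to this:

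- It is not aimed at what the rmANOVA assumes, which is roughly normal residuals and sphericity.
- It covers three assessments and several outcomes with no rule for a split result, so SCS and another score could end up with different questions answered.
- It fires readily on whole-number scores, and more often as the sample grows.

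At stake is the Aim 2 superiority claim on the scores. If both arms improve, a significant Friedman result could be read as a treatment effect. If the arms truly differ but the average over visits is flat, the difference could be missed.

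**Working it through.** **Inputs from the documents.** Two randomised arms; k = 3 assessments (pre-implementation, 1 month, 6 months); alpha 0.05 ("Significance for statistical tests will be set at" 0.05, sidedness not given). The text gives no Aim 2 sample size, SD, correlation or effect size, so there is no figure of the plan's own to reproduce.

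**Step 1: the Friedman test has no arm term (no assumptions needed).** With R_j the rank sum at visit j over n participants, and without tie correction,

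χ² = 12 / [n k (k+1)] × Σ R_j² − 3n(k+1).

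For k = 3 this is Σ R_j² / n − 12n, on 2 df. Arm appears nowhere. In one simulated data set χ² = 1.95, so p = exp(−1.95/2) = 0.377 whatever the arm labels. On the same data the rmANOVA group-by-time p was 0.00002 with the true labels and 0.57 with permuted labels.

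**Step 2: the gate can fire when the model is sound.** With exactly normal data and each test at 0.05, treated as independent:

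- three per-visit tests: 1 − 0.95³ = 14.3% (simulated 12-16%);
- six arm-by-visit tests: 1 − 0.95⁶ = 26.5% (simulated 23-28%).

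With normal residuals and a deliberately extreme 3-SD arm effect, the pooled per-visit gate fires in 22%, 47% and 82% of runs at 10, 20 and 40 per arm. The within-cell gate stays at 25-28%. Normality of pooled scores is thus not the rmANOVA's residual assumption.

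**Step 3: how often it fires on whole-number scores.** Assumptions, none in the documents: SCS is an integer 0-10, start 6, SD 2, within-person correlation 0.6, N is the total in two equal arms, and Shapiro-Wilk at 0.05 is pooled over arms at each visit, with any rejection triggering the switch. Across the no-effect and effect scenarios the gate fires in about 33-45% of trials at N=20, 59-87% at N=40 and 90-100% at N=60.

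**Step 4: what the plan then concludes.** Same assumptions. Changes are from pre-implementation to both follow-ups. The ANCOVA is the 6-month score on arm and baseline.

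| Truth | N | Plan significant | ANCOVA significant |
|---|---|---|---|
| Both arms +1, no arm effect | 40 | 79% | about 5% |
| Both arms +1, no arm effect | 60 | 98% | about 5% |
| Control −0.75, treatment +0.75 | 40 | 32% | 79% |
| Control −0.75, treatment +0.75 | 60 | 13% | 93% |
| Control 0, treatment +1.5 | 40 | 59% | about 79% |
| Control 0, treatment +1.5 | 60 | 77% | about 93% |

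In the last two rows a plan rejection may reflect only change over time. In the −0.75/+0.75 case the ungated group-by-time test has power of about 74-75% (N=40) and 90-91% (N=60), so the loss is not an artefact of choosing ANCOVA as comparator.

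**Step 5: the missing rule matters.** At N=40 the three Shapiro-Wilk tests disagree in 58-75% of trials. With both arms improving by 1 point, the plan declares significance in 79% of trials if any rejection triggers the switch, but in 16% if all three must reject. At N=60 the figures are 98% and 53%.

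**Step 6: separate the gate from the Friedman test.** Keep the gate and replace only the fallback by a Mann-Whitney test on change from baseline:

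- Equal improvement: significant in 4.6% (N=40) and 4.8-5.1% (N=60).
- −0.75/+0.75: power 71-78% (N=40) and 86-93% (N=60), the range covering change to 6 months and mean follow-up change. Against ANCOVA the loss is 79 − 78 = 1 to 79 − 71 = 8 points, and 93 − 93 = 0 to 93 − 86 = 7 points. A repeat run gave 4-9 points against ANCOVA and 2-5 against the ungated rmANOVA.

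**The case against.** The strongest reply is that the damage belongs to the Friedman test and not to pre-testing. Step 6 bears this out. A reader might infer that the gate is seriously harmful in its own right, whatever the fallback. The calculations do not support that: with a valid two-group rank fallback, type I error stays near 5% and the power cost is small.

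Other parts of the reply also stand:

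- Normality within arm and visit does bear on the rmANOVA's residuals, so the gate is not unrelated to the model. It is simply not a test of the model's assumptions as written.
- The SAP says only data. Raw and pooled scores are a reading of it, and the simulation adopts that reading.
- A power figure taken only from −0.75/+0.75 would be unfavourable to the plan, since the average time effect is then zero. The 0/+1.5 case is shown for that reason.
- Normality pre-testing is common, and both branches are stated in advance. That would be a fair defence if both branches compared the arms. Running Friedman separately within each arm would not help, as it still gives no between-arm test.

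A reader might also fault the SAP for not gating visit count and visit time. That is not a supportable criticism here: an ungated, pre-specified comparison is what this point asks for. Whether a t-test suits possibly skewed outcomes is a different question.

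**Conclusion.** The point holds for the clinical outcome scores. Followed as written, the SAP lets a Shapiro-Wilk result choose between an analysis that compares the arms and one that cannot, with no rule for split results. That the Friedman test lacks an arm term depends on no assumption.

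The sizes do depend on assumptions. With the inputs in step 3, equal improvement in both arms is declared significant in about 79% (N=40) and 98% (N=60) of trials. A true 1.5-point difference leads to rejection in 32%/13% or 59%/77%, against about 79%/93% for ANCOVA. A different N, scale, SD, correlation or trigger rule would change these figures. Nearly all of the harm runs through the Friedman branch, so it should be counted once if that test is also criticised separately.

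Two stronger readings go too far. A reader might infer that Aim 2 may contain no between-arm comparison at all; the t-test on visit count and visit time is unconditional. A reader might also infer that the switch will usually divert SCS from the rmANOVA; that depends on a sample size and score distribution the documents do not give, and at N=20 the assumed gate fires in fewer than half of trials.

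**What to change.** Delete both the Shapiro-Wilk decision rule and the Friedman branch from the Aim 2 section. Pre-specify one between-arm analysis for SCS whatever its distribution: a linear or mixed model of the 1-month and 6-month scores on arm, with the pre-implementation score as covariate. Other valid between-arm models exist; what matters is that one is fixed in advance. Use residual plots as diagnostics only, and keep the histograms and boxplots as description. Name one between-arm permutation, rank or robust-variance analysis as a fixed sensitivity analysis, reported whatever the diagnostics show.

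This changes SAP wording only and needs no new data. The cost is one extra sensitivity analysis. The t-test on visit count and visit time need not change on account of this point.
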